**CONFIDENTIAL**

Version Date:

05SEP2022

- 38.0 - 38.9
  - 39.0 - 39.9
  - $\geq 40.0^{\circ}$
- $<38.0, \geq 38.0^{\circ}\text{C}$  (i.e., 'no fever' versus 'fever')

Fever, defined as a body temperature of  $\geq 38^{\circ}\text{C}$  irrespective of route of measurement, will be integrated to the summaries as a systemic AE.

The analyses will encompass summaries of the data on five levels:

1. Daily reports of participants with solicited events.
2. Time of first onset of solicited events.
3. Solicited events, maximum event severity (i.e., severity grading scale as defined in Appendix 4 of the protocol) by event and interval Day 1 - 3, Day 4 - 7, and Day 1 - 7.
4. Duration of solicited events, excluding ongoing solicited events after Day 7.
5. Solicited events and indicators of solicited events, occurrence of at least one event by category (administration site, systemic) and interval Day 1 - 3, Day 4 - 7, Day 1 - 7 and extending beyond Day 7.

For studies using electronic diaries for the collection of solicited events, a solicited event will be considered present only when a daily recording of grade 1 or more is present. For each of the time points or time intervals presented in the summaries, only participants with at least one observation for the solicited events in the interval of interest will be considered.

The analysis of solicited events after first vaccination will be reported separately from the analyses of solicited events after second vaccination. When the occurrences of solicited events are summarized, each event recorded as having occurred during a specific period will be counted as only one occurrence regardless of the number of days on which it occurs

Level 1: Daily reports of solicited events

For each of the time points, only participants with at least one observation for the solicited events in the

---

Document: C:\ProgramData\activePDF\Temp\DocConverter\API\Input\99638a57dafd\$76D9DDEF7D8D4E7C  
B4DEE6C228977964.docx

Author: PPD

Version Number:

Final 5.0

**CONFIDENTIAL** Version Date:

05SEP2022

interval of interest will be considered. Data collected will be summarized (frequencies and percentages of participants) by vaccine group, solicited events, vaccination number and time point.

#### Level 2: Time of first onset of solicited events

The time of first onset is defined, for each participant, for each solicited event, as the time point at which the respective solicited event first occurred. For erythema, swelling and induration the following threshold will be used  $\geq 25$  mm. The summary will provide the frequencies and percentages of participants with first onset of each solicited events by vaccine group and vaccination number, and by each time point.

For each vaccination the first onset of the AE will be used for each participant. For any vaccination the worst AE across all vaccinations per time point will be used. Note, 'not done' is treated identical to 'missing'.

#### Level 3: Solicited events, maximum event severity by event and interval

The maximum event severity will be defined if there is at least one non-missing observation within this time interval, each participant's data will be aggregated across the time points of the interval and summarized according to the maximal severity observed for each adverse event, followed by a summary across participants for each vaccine group and vaccination. Participants without any solicited events in the interval, i.e., missing values at each of the requested time points, will be removed from the denominator.

#### Level 4: Number of days with solicited events

The duration of an event with a start and end date will be the number of days between the start and end dates plus one day, i.e. an event that starts on 03MAR2018 and ends on 12MAR2018 has a duration of 10 days.

The number of days with the AE is defined irrespective of severity. This means at least 'mild' solicited events that are assessed qualitatively  $\geq 25$ , mm for erythema, swelling and induration. If a solicited event continues beyond Day 7 the period after Day 7 is not added.

---

Document: C:\ProgramData\activePDF\Temp\DocConverter\API\input\99638a57dafd\$76D9DDEF7D8D4E7C  
B4DEE6C228977964.docx

Author: PPD

Version Number: Final 5.0

**CONFIDENTIAL** Version Date: 05SEP2022

The frequency distribution of the number of days will be provided in a summary table by vaccine group and vaccination, and by AE.

Level 5: Solicited events, occurrence of at least one event by category (administration site, systemic) and interval.

The occurrence of at least one solicited event is defined as “any” for a participant if he/she reports greater than “none”  $\geq 25$  mm, for erythema, swelling and induration for the respective event and “none” otherwise. The occurrence of at least one solicited event (i.e., none versus any) will be summarized by category (i.e., administration site, systemic, any), by vaccine group, by vaccination (after each vaccination and after any vaccination) and by time interval.

Use of antipyretics and analgesics to treat or prevent pain or fever will be summarized by frequencies and percentages of participants reporting use of the medications by type of use (prophylactic versus treatment) and for Day 1 - Day 3, Day 4 - 7, Day 1 - Day 7.

### 17.1.3. UNSOLICITED ADVERSE EVENTS

The unsolicited AEs will be summarized per the USS.

All the unsolicited AEs occurring during the study, judged either as probably related, possibly related, or not related to vaccination by the investigator, will be recorded. The original verbatim terms used by investigators to identify adverse events in the CRFs will be mapped to preferred terms using the MedDRA dictionary. The unsolicited AEs will then be grouped by MedDRA preferred terms into frequency tables according to system organ class. AEs judged by the investigator as at least possibly related to study vaccine will be summarized by vaccine group, according to system organ class and preferred term within system organ class. When an unsolicited AE occurs more than once for a participant, the maximal severity and strongest relationship to the vaccine group will be counted.

The dose relative to an event is the most recent study dose given to a participant prior to the start of a given event. For example, if the start date of an adverse event is between the first vaccination and the second vaccination, the relative dose will be the first vaccination.

---

Document: C:\ProgramData\activePDF\Temp\DocConverter\API\input\99638a57dafd\$76D9DDEF7D8D4E7C  
B4DEE6C228977964.docx

Author: PPD

Version Number: Final 5.0

**CONFIDENTIAL** Version Date: 05SEP2022

If an event starts on the same day as a study dose, the relative dose will be derived from the additional information provided in the CRF using the contents of the flag indicating if the event occurred before or after vaccination. If 'after vaccination' is selected, the relative dose for the event will be the one administered on the start day of the event. If 'before vaccination' is selected, the relative dose for the event will be the dose prior to this one.

If an adverse event start date is missing or unknown, the AE will be considered as to have started after the first vaccination. For partially available dates, refer to APPENDIX 2.

Only adverse events with a start date on or after the first vaccination will be analyzed, i.e., excluding those after a participant has given informed consent but before the first vaccination. The selection of unsolicited AEs and the assignment to time intervals will be done by day of onset and not by days ongoing/persisting. AEs starting prior to the first vaccination, if any, will only be listed.

For each of the following intervals any unsolicited AE will be summarized:

- after each vaccination (from Day 1 to Day 31 and from Day 181 to Day 211, separately)
- after any vaccination (Day 1-31 and Day 181-211):
- entire study (Day 1 to end of study)

The following unsolicited adverse events will be summarized during the entire study:

- Possibly or probably related unsolicited AEs.
- Unsolicited AEs leading to death will be listed.
- Serious adverse events (SAEs).
- Possibly or probably related SAE.
- Possibly or probably related SAE leading to death
- Unsolicited AEs leading to premature withdrawal from study.
- Unsolicited AEs leading to discontinuation or delay in study vaccination.
- Unsolicited adverse events of special interest (AESI), as recorded on the Expedited AE report.
- Medically attended AEs.

---

Document: C:\ProgramData\activePDF\Temp\DocConverter\API\input\99638a57dafd\$76D9DDEF7D8D4E7C  
B4DEE6C228977964.docx

Author: PPD

Version Number:

Final 5.0

**CONFIDENTIAL** Version Date:

05SEP2022

Note: All the information required for the unsolicited AE summaries, including AESIs and medically attended AEs will be collected on the eCRF AE Form. Solicited events starting more than 7 days after the vaccination will also be considered as unsolicited AEs.

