Visit 1 to Visit 3	180 days	175 to 194 days (-5 to +14 days)
Visit 3 to Visit 4	30 days	25 to 44 days (-5 to +14 days)
Visit 3 to Last Telephone Contact (T5)	180 days	173 to 201 days (-7 to +21 days)

T = telephone contact

Table 5 Intervals Between Telephone Contacts

Interval	Length of Interval	Allowed Interval (Range)
Visit 1 to Telephone contact T1	14 days	11 to 17 days (-3 to +3 days)
Visit 1 to Telephone contact T2	90 days	87 to 93 days (-3 to +3 days)
Visit 3 to Telephone contact T3	14 days	11 to 17 days (-3 to +3 days)
Visit 3 to Telephone contact T4	90 days	87 to 93 days (-3 to +3 days)
Visit 3 to Last Telephone contact (T5)	180 days	173 to 201 days (-7 to +21 days)

T = telephone contact

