In addition to the above-mentioned reporting requirements and in order to fulfill international reporting obligations, SAEs that are related to study participation (i.e., protocol-mandated procedures, invasive tests, a change from existing therapy) or are related to a concurrent GSK medication/vaccine will be collected and recorded from consent until the participant is discharged from the study. Details regarding follow-up of AEs, SAEs, and AESIs are provided in [Appendix 4](#).

An overview of the protocol-required reporting periods for solicited administration site and systemic events, unsolicited AEs, medically attended AEs, AEs leading to vaccine/study withdrawal, SAEs, AESIs, SAEs related to study participation or concurrent GSK medication/vaccine and pregnancy is provided in [Table 12](#).

Table 12 Timeframes for Collecting and Reporting of Safety Information

Time Points	Pre-Vacc¹	Vacc 1	Post-Vacc 1	PC	Post-Vacc 1	PC		Vacc 2	Post-Vacc 2	PC	Post-Vacc 2	PC	PC
Visit	-	V1		T1	V2	T2		V3		T3	V4	T4	T5 ESFU
Day	-	D1	D7²	D15	D31³	D91		D181	D187²	D195	D211³	D271	D361
Month	-	M0	M0		M1	M3		M6	M6		M7	M9	M12
Solicited administration site and systemic events ^{4,5}													
All unsolicited AEs ^{4,6}													
AEs leading to intervention/study withdrawal ^{4,6}													
Medically attended AEs ^{4,6}													
SAEs ^{4,6}													
AESIs ⁴													

Time Points	Pre-Vacc¹	Vacc 1	Post-Vacc 1	PC	Post-Vacc 1	PC		Vacc 2	Post-Vacc 2	PC	Post-Vacc 2	PC	PC
Visit	-	V1		T1	V2	T2		V3		T3	V4	T4	T5 ESFU
Day	-	D1	D7²	D15	D31³	D91		D181	D187²	D195	D211³	D271	D361
Month	-	M0	M0		M1	M3		M6	M6		M7	M9	M12
SAEs related to study participation or concurrent GSK medication/vaccine ^{4,6}													
Pregnancy													

AEs = adverse events; AESIs = adverse events of special interest; D = day; ESFU = extended safety follow-up; M = month; PC = phone contact; SAE = serious adverse event; T = telephone call; V = visit; Vacc = vaccination.

- ¹ Consent obtained.
- ² Seven consecutive days post-vaccination (including the day of vaccination).
- ³ Thirty consecutive days post-vaccination (including the day of vaccination).
- ⁴ All concomitant medications/products, except vitamins and dietary supplements, administered to treat an AE/SAE, occurred during the entire study period (Day 1 to Day 361), should be recorded in the eCRF and participant’s medical records.

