9.4.3.2.2 Unsolicited AEs

These analyses will be performed on the unsolicited safety set.

The frequencies and percentages of participants with any unsolicited AEs (including all SAEs, AEs leading to withdrawal, AESIs and medically attended AEs [see all relevant AE definitions in [Appendix 1](#), Glossary of Terms]) during the 7 and the 30 days (including the day of vaccination) following vaccination at Day 1 and Day 181 will be presented.

The frequencies and percentages of participants with SAEs, AEs leading to withdrawal, AESIs and medically attended AEs throughout the study period will be presented.

This analysis applies to all AEs occurring during the study, judged either as probably related, possibly related or not related to vaccination by the investigator, recorded in AE eCRF, with a start date on or after the date of first vaccination ([Table 12](#)). AE starting prior to the first vaccination will only be listed. The original verbatim terms used by investigators to identify AEs in the eCRFs will be mapped to preferred terms (PTs) using the Medical Dictionary for Regulatory Activities (MedDRA) dictionary. The AEs will

then be grouped by MedDRA PTs into frequency tables according to system organ class (SOC).

All reported AEs, as well as AEs judged by the investigator as related to study vaccine, will be summarized according to SOC and PT within SOC. These summaries will be presented by vaccine group and by interval of study observation. When an AE occurs more than once for a participant, the maximal severity and strongest relationship to the vaccine group will be counted.

Separate summaries will be produced for the following categories:

- SAE
- AE related to vaccine
- AESI
- AE leading to withdrawal
- AE leading to a medically attended visit

Data listings of all AEs will be provided by participant. In addition, AEs in the categories above will be provided as listed data.

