#### 2.5.4. PRIMARY SAFETY ENDPOINTS

The safety and reactogenicity of the MenABCWY and MenACWY vaccines will be demonstrated for participants in the corresponding Safety Sets (as defined in Sections 0, 5.6.2 and 5.6.3) from:

- The frequencies and percentages of participants with solicited administration site events (i.e., injection site pain, erythema, swelling, induration) and solicited systemic events (i.e., fever [body temperature  $\geq 38.0^{\circ}\text{C}/100.4^{\circ}\text{F}$ ], nausea, fatigue, myalgia, arthralgia, headache) during the 7 days (including the day of vaccination) following vaccination at Day 1, Month 0 (for the ABCWY and ACWY groups) and Day 181, Month 6 (for the ABCWY group).
- The frequencies and percentages of participants with any unsolicited AEs (including all SAEs, AEs leading to withdrawal, AESIs and medically attended AEs) during the 30 days (including the day of vaccination) following vaccination at Day 1, Month 0 (for the ABCWY and ACWY groups) and Day 181, Month 6 (for the ABCWY group).
- The percentages of participants with SAEs, AEs leading to withdrawal, AESIs and medically attended AEs throughout the study period (Month 0 to Month 12).

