### 6.1. REFERENCE START DATE AND STUDY DAY

Study Day will be calculated from the reference start date and will be used to show start/stop day of assessments and events.

Reference start date is defined as the day of the first dose of study medication, (Day 1 is the day of the first vaccination).

- If the date of the event is on or after the reference date then:
  - Study Day = (date of event – reference date) + 1.

In the situation where the event date is partial or missing, Study Day, and any corresponding durations will appear partial or missing in the data listings.

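### SAP 17.1.3 summarises unsolicited AEs over 31-day intervals although the primary safety endpoint is 30 days, and it omits the protocol's 7-day interval without declaring the change

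*SAP*

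**What the plan says.** **Endpoint.** The unsolicited-AE component of the primary safety endpoint, in SAP 2.5.4 and identically in the protocol synopsis and Table 6, covers every kind of unsolicited event. Its window is worded "AESIs and medically attended AEs) during the 30 days (including the day of vaccination) following vaccination at Day 1, Month 0". That part applies to both groups; the matching part after the Day 181 vaccination applies to ABCWY alone.

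**Collection.** The schedule of activities (protocol Table 3) records unsolicited AEs for Days 1-30 after vaccination. Protocol 8.3.6.1 says the same. It collects SAEs, AESIs, medically attended AEs and AEs leading to withdrawal throughout the study. Footnote 3 of protocol Table 12 reads "Thirty consecutive days post-vaccination (including the day of vaccination", but it is attached to the columns headed D31 and D211.

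**Planned analysis.** Protocol 9.4.3.2.2 presents unsolicited AEs "during the 7 and the 30 days (including the day of vaccination) following vaccination at Day 1 and Day 181". The synopsis lists the same two intervals.

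**SAP intervals.** SAP 17.1.3 lists "after each vaccination (from Day 1 to Day 31 and from Day 181 to Day 211, separately", then "after any vaccination (Day 1-31 and Day 181-211", then the entire study. No 7-day interval appears. Events are assigned to intervals by onset day. A separate rule in the same section takes the relative dose to be the most recent dose before onset, and a before/after-vaccination flag settles events that start on a dosing day.

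**Declared changes.** SAP 3.3 declares the wider visit window for analysis and states that there are no other changes to the protocol's planned analyses.

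**The concern.** A table meant to report a primary safety endpoint should use that endpoint's window. Here the SAP defines one window in 2.5.4 and tabulates another in 17.1.3.

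The surplus day is also not like the other thirty. Routine unsolicited AEs fall outside their collection period on that day, while the event types followed for the whole study remain inside theirs, so ascertainment is uneven. For the second dose, the surplus day is nominally the day of the third injection (saline in ABCWY, MenB in ACWY).

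Separately, an interval that the protocol planned is missing from the SAP text while the SAP states that nothing else has changed. A reader of the study report could not tell whether the omission was deliberate.

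**Working it through.** **Inputs**
- Day of first vaccination = Day 1; study day = date difference + 1 (SAP 6.1).
- Endpoint length: 30 days, vaccination day counted (protocol Table 6, SAP 2.5.4).
- SAP intervals: Day 1-31 and Day 181-211 (SAP 17.1.3).
- Visit 3 to Visit 4: nominally 30 days, allowed "25 to 44 days (-5 to +14 days" (protocol Table 4).

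**Step 1: check the counting rule on a window the SAP gets right.** Length = last day − first day + 1. SAP 17.1.2 writes the 7-day solicited window as Day 1 to 7 and Day 181 to 187:
- 7 − 1 + 1 = 7
- 187 − 181 + 1 = 7

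The rule reproduces the stated 7 days.

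**Step 2: apply it to the 30-day endpoint.** The last day is the first day + 29:
- 1 + 29 = 30, so Day 1-30
- 181 + 29 = 210, so Day 181-210

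**Step 3: apply it to the SAP's unsolicited intervals.**
- 31 − 1 + 1 = 31
- 211 − 181 + 1 = 31

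Each is one day too long, and 1/30 = 3.3%. The intervals reach 30 days only if the vaccination day is left out (31 − 1 = 30; 211 − 181 = 30), but the endpoint text counts that day.

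**Step 4: overlap with the Visit 4 injection, counted from the actual second dose.** If Visit 4 is k days after Visit 3, it falls on day k + 1 after the dose. A window of L days therefore contains max(0, L − k) days on or after the third injection.

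| Visit 4 at | 31-day window (SAP) | 30-day window (protocol) |
|---|---|---|
| k = 30 (nominal) | 31 − 30 = 1 | 30 − 30 = 0 |
| k = 25 (earliest allowed) | 31 − 25 = 6 | 30 − 25 = 5 |

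At both timings the SAP adds one day. The other five at k = 25 come from the protocol's own endpoint and visit window.

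**Step 5: 7-day interval.** Protocol 1.1 and 9.4.3.2.2 plan 7-day and 30-day summaries. SAP 17.1.3 lists two intervals after vaccination, their union and the entire study. The 7-day summary is absent from the SAP text and from the changes declared in SAP 3.3.

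**The case against.** **The error is one day, and the protocol shares it.** Both points stand. Table 12 puts its 30-day footnote under D31 and D211, which probably explains the SAP's end days. This limits the size of the point and means that both documents need reconciling. It does not make 31 days equal 30.

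**The SAP already has a relative-dose rule and a same-day flag.** This also stands in part. Under that rule an event after the Visit 4 injection belongs to the third dose, so a reader should not infer that such events are definitely attributed to the second vaccination. But intervals are filled by onset day, and the SAP does not say how the two rules combine.

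**The 7-day table is not part of the primary endpoint.** True: it is descriptive. The table shells were also not available for review, so only its absence from the SAP text can be claimed.

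**Stronger readings.** Because "Study Day will be calculated from the reference start date", a reader might infer that Day 181-211 means fixed study days, so that participants with an early or late Visit 3 lose part of their follow-up after the second dose. The documents do not support treating this as the plan. The solicited window of Day 181 to 187 is plainly nominal, both documents use Day 181 and Day 211 as visit labels, and the bullet itself says the interval follows each vaccination. The wider windows in SAP Table 2 are for immunogenicity only and do not set AE intervals.

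A reader might also infer that the primary endpoint mixes different products across arms. It does not: its Day 181 component covers ABCWY only, whose third injection is saline. Protocol 4.2 attaches no objective to MenB, and SAP 17 plans no between-group safety comparisons unless otherwise specified.

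**Conclusion.** The point holds as a mismatch of definitions. SAP 17.1.3 tabulates 31 days against a 30-day primary safety endpoint and collection period. The surplus day of the second interval is the nominal Visit 4 injection day, and routine unsolicited AEs are not systematically collected for it. The planned 7-day interval is missing from the SAP text and its removal is not declared.

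The one-day excess is probably small numerically; the documents give no event rates from which to put a figure on it. No sample size, power or alpha depends on it. The day counts rest on the SAP's Day 1 convention and the overlap counts on the visit intervals in protocol Table 4. The conclusion does not depend on a literal study-day reading, although the SAP should state its anchor. The correction is worth making because it is cheap and the present text contradicts the SAP's own endpoint definition.

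**What to change.** - **SAP 17.1.3, each vaccination:** define the interval as the actual date of that vaccination (day 1) through day 30. Build the after-any-vaccination interval from the same rule.
- **7-day interval:** add day 1-7 after each of the Day 1 and Day 181 vaccinations, or declare its removal in SAP 3.3 with a reason.
- **Events after the Visit 4 injection:** keep the protocol's 30-day endpoint. State that events starting after that injection but within 30 days of the second vaccination are identified by the existing relative-dose rule and before/after flag, and shown separately. Cutting every interval at the next injection is not advised: with Visit 4 at 25 days it would shorten the endpoint to 25 days and create a new departure from the protocol.
- **Protocol Table 12:** reconcile the D31 and D211 labels with the 30-day footnote.

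Cost: SAP wording, one interval derivation, one extra descriptive table and a label correction. If the programming already counts 30 days from the actual dose date, the interval change is wording only. No new data are needed.

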Recording of unsolicited adverse events (Days 1-30 post-vaccination)	●	●	●		●	●	●		
Return and review of eDiaries			○				○		
Recording of any AEs leading to vaccine/study withdrawal ⁸	●	●	●	●	●	●	●	●	●

Age	15 to 25 Years (25 Years + 364 Days) at Study Start								
Type of contact	Visit	PC	Visit	PC	Visit	PC	Visit	PC	PC
Visit/phone contact ¹	V1	T1	V2	T2	V3	T3	V4	T4	T5
Time points	D1 M0	D15	D31 M1	D91 M3	D181 M6	D195	D211 M7	D271 M9	D361 (ESFU)
Visit window (days)	n/a	(-3/+3)	(-5/+14)	(-3/+3)	(-5/+14)	(-3 /+3)	(-5/+14)	(-3/+3)	(-7/+21)
Days post-vaccination ²	0	14 post-vacc 1	30 post-vacc 1	90 post-vacc 1	180 post-vacc 1	14 post-vacc 2	30 post-vacc 2	90 post-vacc 2	180 post-vacc 2
Sampling time points	pre-vacc		post-vacc 1				post-vacc 2		
Recording of medically attended AEs	●	●	●	●	●	●	●	●	●
Recording of SAEs	●	●	●	●	●	●	●	●	●
Recording of AESIs	●	●	●	●	●	●	●	●	●
Recording of SAEs related to study participation, or to a concurrent GSK medication/vaccine ¹²	●	●	●	●	●	●	●	●	●
Recording of COVID-19 related AEs and SAEs ¹³	●	●	●	●	●	●	●	●	●
Recording of pregnancies	●	●	●	●	●	●	●	●	●
Study Conclusion ¹⁴									●

● study procedure that requires documentation in the individual eCRF.

○ study procedure that does not require documentation in the individual eCRF. Documentation will be required in the source documents

× study procedure that requires documentation in the study eDiary

The double-line border following D211 indicates the analyses which will be performed on all data (i.e., the data that are as clean as possible) obtained up to D211.

AE = adverse event; AESI = adverse events of special interest; COVID-19 = coronavirus disease 2019; D = day; eCRF = electronic case report form; eDiary = participant diary (electronic diary); ESFU = extended safety follow-up; GSK = GlaxoSmithKline Biologicals; M = month; PC = phone contact; post-vacc = post-vaccination; pre-vacc = pre-vaccination; T = telephone contact; SAE = serious adverse event; V = visit

¹ Home visits are always allowed if deemed suitable and are conducted according to local regulations.

² Days post-injection are included to keep track of the intercurrent days between vaccinations, they do not indicate “Study Day”

³ Confirm consent form and informed assent form (if applicable) signed prior to any procedures.

- ⁴ Procedure to be performed prior to any vaccination.

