8.3.6 Adverse Events

8.3.6.1 Time Period and Frequency for Collecting AE and SAE Information

Solicited administration site and systemic events occurring during the 7 days (including the day of vaccination) following vaccination at Day 1 and Day 181, will be collected using a pre-defined participant eDiary (refer to the SoA [[Table 3](#)]). See [Appendix 1](#),

Glossary of Terms, for definitions of various types of AEs and to [Appendix 4](#) for further details on solicited AEs. Solicited administration site and systemic events that are ongoing after the 7-day reporting period will continue to be recorded in the eDiary until resolution or up to 30 days post-vaccination (i.e., recording period for unsolicited AEs) whichever occurs first and do not need to be entered as an AE in the AE eCRF or the participant's source document.

Any solicited AE that has not resolved within 30 days post-vaccination and is reported during clinic visits or safety follow-up calls will be entered into the subject's eCRF as an unsolicited AE. It will also be included in the subject's source documents at the site by the investigator/site staff as a verbally reported event. It will not be included in the Subject eDiary. These AEs will be analyzed as unsolicited AEs (i.e., in the Unsolicited Safety Set).

Unsolicited AEs are AEs that are not solicited using a participant eDiary occurring during the 30 days (including the day of vaccination) following vaccination at Day 1 and Day 181 (refer to the SoA [[Table 3](#)]), and must be recorded in the appropriate section of the eCRF, irrespective of intensity or whether or not they are considered vaccination-related.

The time period for collecting and recording AEs leading to vaccine/study withdrawal, medically attended AEs, SAEs, pregnancies, and AESIs will begin at Day 1 (i.e., the first receipt of study vaccines) and will end 6 months following administration of the last dose of investigational vaccine for each participant (i.e., study end). Refer to [Section 8.3.6.4](#) for instructions on reporting of SAEs, pregnancies, and AESIs.

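### The SAP's entire-study tables for any, and for related, unsolicited AEs mix full collection (two 30-day windows) with selective collection (the rest of the year), so they estimate neither a window rate nor a 12-month rate

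*SAP*

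**What the plan says.** **Collection (protocol).** Section 8.3.6.1 defines the general category by its window, as events that the diary does not ask about: "occurring during the 30 days (including the day of vaccination) following vaccination at Day 1 and Day 181". The Schedule of Activities (Table 3) labels the row "Recording of unsolicited adverse events (Days 1-30 post-vaccination". It marks that row at Visits 1 to 4 and at telephone contacts T1 and T3, and leaves it blank at T2 (Day 91), T4 (Day 271) and T5 (Day 361). Table 12, footnote 3, attached to the Day 31 and Day 211 columns, gives thirty consecutive days including the day of vaccination.

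A separate rule covers the selected categories: "The time period for collecting and recording AEs leading to vaccine/study withdrawal, medically attended AEs, SAEs, pregnancies, and AESIs will begin at Day 1". That collection runs to study end.

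**Analysis (protocol).** For the whole study, section 9.4.3.2.2 names only those categories: "The frequencies and percentages of participants with SAEs, AEs leading to withdrawal, AESIs and medically attended AEs throughout the study period will be presented".

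**Analysis (SAP 17.1.3).** The lead-in is "For each of the following intervals any unsolicited AE will be summarized". The intervals that follow are each post-vaccination window, the two windows combined, and "entire study (Day 1 to end of study". A second list opens "The following unsolicited adverse events will be summarized during the entire study", and its first item is unsolicited AEs judged possibly or probably related. No other interval is stated for that item. The same section also says that all unsolicited AEs arising during the study will be recorded.

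**The concern.** A table can describe only what was collected. The SAP gives general unsolicited AEs an interval of about 12 months, while the protocol looks for them in two windows of about one month each. A reader of the clinical study report would take the entire-study row as the proportion of participants with any unsolicited AE over the year. It would in fact hold every reported AE from the two windows plus a filtered subset from the rest of the year. It would be higher than the window rate and lower than the 12-month rate, by an amount nobody can recover from the table.

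The related-AE summary is more exposed, because section 17.1.3 states no window version of it to fall back on.

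The entire-study rows also span the period after the Day 211 injection, when the ACWY group receives MenB and the ABCWY group receives saline. No general unsolicited AE window is attached to that injection.

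**Working it through.** The plan gives no figure to reproduce, so the check compares the collection rule with the tabulation rule and then illustrates the size.

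**Step 1: days covered.** Inputs: two windows of 30 inclusive days (protocol 8.3.6.1) and a study running from Day 1 to Day 361 (Table 3).
- General collection: 2 × 30 = 60 days, and 60/361 = 16.6%.
- Selected categories only: 361 − 60 = 301 days.
- With the SAP's own windows (Day 1 to 31 and Day 181 to 211, 31 inclusive days each): 62/361 = 17.2%, leaving 299 days.

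**Step 2: the Day 211 injection.** The second window runs from Day 181 to Day 210. On the nominal schedule it closes the day before the Visit 4 injection. Visit 4 may take place 25 to 44 days after Visit 3 (Table 4). The earliest permitted date is therefore Day 206, counting from a Day 181 Visit 3, which gives an overlap of at most five days (206 to 210).

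**Step 3: what each table would contain.**

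| SAP table | Collection behind it | Matches its label? |
|---|---|---|
| Any unsolicited AE, each window and both combined | General collection | Yes, apart from 31 days against 30 |
| SAEs, AESIs, medically attended AEs, AEs leading to withdrawal, entire study | Day 1 to study end | Yes |
| Any unsolicited AE, entire study | General for 60 days, selective for 301 | No |
| Related unsolicited AEs, entire study | General for 60 days, selective for 301 | No |

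**Step 4: illustration of size.** The inputs here are assumptions, not document figures: a constant AE hazard, a probability r of at least one AE in 30 days, and a share m of AEs that fall in the selected categories.
- Hazard: λ = −ln(1 − r)/30.
- Row as tabulated: 1 − exp(−λ(60 + 301m)).
- Full collection: 1 − exp(−361λ).

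For r = 10% and m = 0.1, the exponent covers 60 + 30.1 = 90.1 days, and 1 − 0.9^(90.1/30) = 27.1%. Full collection gives 1 − 0.9^(361/30) = 71.9%.

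| r per 30 days | Two windows only (m = 0) | Row, m = 0.1 | Row, m = 0.3 | Row, m = 0.5 | Full collection (m = 1) |
|---|---|---|---|---|---|
| 10% | 19.0% | 27.1% | 41.0% | 52.3% | 71.9% |
| 20% | 36.0% | 48.8% | 67.3% | 79.1% | 93.2% |
| 30% | 51.0% | 65.7% | 83.3% | 91.8% | 98.6% |

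The row equals the window rate only if m = 0 and the full-collection rate only if m = 1.

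**The case against.** The strongest reply is that the protocol itself is broad in places. Section 9.4.3.2.2 goes on to say that the analysis covers all AEs arising in the study, and it plans summaries of all reported and all related AEs by observation interval. The glossary definition of an unsolicited AE carries no 30-day limit. On that reading the SAP is carrying out the protocol. Part of this stands. A reader might infer that the SAP made an undeclared change, since SAP section 3.3 lists only the visit windows, but with wording this loose the documents do not establish that. It does not rescue the tables, however: the broad sentence cites Table 12, which carries the 30-day limit, and a wide definition cannot supply data the schedule does not collect.

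Two other stronger readings are not supported:
- A reader might compare the window-only rate with the 12-month rate (19% against 72% at r = 10%) and call that the shortfall. The disputed row also includes the selected categories throughout, so the gap is smaller.
- A reader might infer that the content outside the windows depends on site habit. Such events enter by written rule: the four categories, solicited events unresolved at 30 days (8.3.6.1), and abnormal findings at symptom-directed examinations (8.3.2). Nothing invites discretionary recording.

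It is also fair to say that the collection rules are the same in both groups, that SAP section 17 plans no statistical safety comparison unless specified, and that the sound window tables are planned as well. Titles and footnotes in the table shells, which are not among the documents reviewed, might already state the ascertainment. These points limit the consequence, but they do not correct the rule written in section 17.1.3.

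**Conclusion.** The point holds as a fault in two descriptive summaries. Followed as written, the entire-study rows for any and for related unsolicited AEs combine full ascertainment on 60 of 361 days with selective ascertainment on 301. The SAP's statement that all unsolicited AEs in the study will be recorded contradicts protocol 8.3.6.1 and Table 3.

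Only the day counts come from the documents. The size of the shortfall rests on an assumed constant hazard, AE risk and share of selected events. It should be read as showing that the gap can be large (about 27% to 52% shown against about 72%, at 10% per 30 days and a 10% to 50% share), not as an estimate for this trial.

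The different injections at Day 211 might lead a reader to infer a between-group bias. The documents show only that general AEs after an active vaccine in one group and saline in the other go largely uncollected. They give no basis for the size of any imbalance.

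The primary safety endpoints keep the correct split in both documents (protocol Table 6, SAP 2.5.4), and the whole-study tables for the four selected categories are sound.

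**What to change.** In SAP section 17.1.3:
1. Restrict the any-unsolicited-AE and related-unsolicited-AE summaries to the two 30-day post-vaccination windows, separately and combined. State the windows as 30 inclusive days, as in the protocol.
2. Over the entire study, tabulate only the categories collected throughout: SAEs, AESIs, medically attended AEs and AEs leading to withdrawal. Show each overall and by relatedness. Simply deleting the whole-study related-AE table would lose late-onset, related, non-serious, medically attended AEs, which are validly collected and appear by relatedness in no other listed table.
3. List, rather than tabulate, any other AEs with onset outside the windows.
4. Correct the sentence on recording so that it follows the collection periods in protocol 8.3.6.1, and align the similar wording in protocol 9.4.3.2.2.

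The cost is SAP wording and table-shell edits, plus the matching clarification in the protocol. No new data are needed and no endpoint changes.
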